# 11.4.2 Secondary Efficacy Endpoints

The incidence of side effects associated HLA-B27-associated uveitis will be compared between treatment groups. The changes in IOP, in central 1 mm subfield thickness, and the changes in OCT will be compared between treatment

Statistical Analysis Plan Version no. 1.0 – 20/07/2020 Protocol Code NORFLO-ORO-16 EudraCT number NA

groups using ANCOVA, with the baseline level included in the model. The presence of keratopathy and synechiae will be compared between treatment groups using chi-square test.

The changes in BCVA and symptoms (ocular pain, blurred vision, floaters and photophobia), measured by VAS, will be compared between treatment groups using ANCOVA, with the baseline level included in the model.

Each information collected through the Quick questionnaire will be compared between the two treatment groups using chi-square test.

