3.2 Secondary Objectives

The secondary objectives of this study include:

- the evaluation of the improvement of side effects due to HLA-B27-associated uveitis such as IOP, cystoid macular edema, keratopathy and synechia;
- the evaluation of the improvement in uveitis-related symptoms (BCVA and symptoms measured by VAS like ocular pain, photophobia, floaters and blurred vision).
- the evaluation of cell damage and inflammation reduction in patients with HLA-B27associated uveitis;
- the evaluation of the patients' attitude towards the study treatment;
- the evaluation of the safety profile of the study product.

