5.2 Secondary Efficacy Endpoints

The following secondary endpoints will be examined:

- The reduction of the side effects due to HLA-B27-associated uveitis, such as IOP assessed by Goldmann applanation tonometry (APL), cystoid macular edema (central foveal thickness central 1 mm subfield thickness), assessed by optical coherence tomography (OCT) Spectralis[®] spectralis, keratopathy, evaluated by fluorescein staining of the cornea (present/absent), and synechiae, assessed by photographic slit lamp (present/absent and if present, involving one or more quadrants; photographs shall be retained to document synechia), after treatment with NORFLO[®] ORO, when compared to placebo.
- The improvement in uveitis-related symptoms (BCVA, symptoms like ocular pain, photophobia, floaters and blurred vision, measured by VAS) after treatment with NORFLO[®] ORO, when compared to placebo.
- The patients' attitude towards the treatment with NORFLO[®] ORO, compared to placebo, will be captured by means of a questionnaire (Quick Questionnaire) specifically developed for the study on the basis of previous experiences^{4,36-39}.

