14.4 Analysis of Secondary Endpoints

The incidence of side effects associated HLA-B27-associated uveitis, such as cystoid macular edema (central 1 mm subfield thickness), keratopathy and synechia, will be compared between treatment groups using logistic regression. In addition, the changes in IOP, in central 1 mm subfield thickness will be compared between treatment groups using ANCOVA, with the baseline level included in the model. The presence of keratopathy and synechiae will be compared between treatment groups using logistic regression. The number of quadrants involved by synechiae, when present, will be described.

The changes in BCVA and symptoms (ocular pain, blurred vision, floaters and photophobia), measured by VAS, will be compared between treatment groups using ANCOVA, with the baseline level included in the model.

Each information collected through the Quick questionnaire will be compared between the two treatment groups using chi-square test.

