### 5.2 Secondary Endpoints

The following secondary endpoints will be examined:

the reduction of the side effects due to HLA-B27-associated uveitis, such as IOP assessed by Goldmann applanation tonometry (APL), cystoid macular edema (central foveal thickness – central 1 mm subfield

Statistical Analysis Plan Version no. 1.0 – 20/07/2020

Protocol Code NORFLO-ORO-16 EudraCT number NA

thickness), assessed by optical coherence tomography (OCT) Spectralis® spectralis, keratopathy, evaluated by fluorescein staining of the cornea (present/absent), and synechiae, assessed by photographic slit lamp (present/absent and if present, involving one or more quadrants; photographs shall be retained to document synechia), after treatment with NORFLO® ORO, when compared to placebo;

the improvement in uveitis-related symptoms (BCVA, symptoms like ocular pain, photophobia, floaters and blurred vision, measured by VAS) after treatment with NORFLO® ORO, when compared to

placebo;

the patients' attitude towards the treatment with NORFLO® ORO, compared to placebo, was captured by means of a questionnaire (Quick Questionnaire) specifically developed for the study on the basis of previous experiences.

These data were reported at visit 1 (baseline), at visit 2 (after 6 months) and at visit 3 (after 12 months). In case of relapse near visit 3, the data collected during the visit 3 will be replaced with the data collected during the first unscheduled visit.

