## 11.5 Summary of Efficacy Analyses

| Endpoint   | Analysis  | Populations |
|--|---|-------------|
| The mean number and intensity of relapses
(primary endpoint)                | Student's t-test, ANOVA, generalized linear mixed model | ITT         |
| The reduction of mean number of relapses (primary endpoint)                    | Student's t-test, ANOVA                                 | ITT         |
| The difference of the level of cell damage and inflammation (primary endpoint) | ANCOVA  | ITT         |
| The changes in IOP (secondary endpoint)  | ANCOVA  | ITT         |
| The changes in OCT (secondary endpoint)  | ANCOVA  | ITT         |
| The changes in BCVA (secondary endpoint)                                       | ANCOVA  | ITT         |
| The presence of keratopathy (secondary endpoint)                               | Chi-square test   | JTT         |
| The presence of synechiae (secondary endpoint)                                 | Chi-square test   | ITT         |
| Information collected through the Quick questionnaire (secondary endpoint)     | Chi-square test   | ITT         |

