# 13. DEVIATIONS FROM THE PROTOCOL SPECIFIED ANALYSIS

The analysis of the number of relapses per eye will not be performed.

Nonparametric test will be used when the variables are not normally distributed.

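### The comparison of keratopathy and synechiae ignores baseline presence, so lesions that predate randomisation can count as outcomes and dilute the treatment contrast

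*SAP*

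**What the plan says.** SAP 11.4.2: "The presence of keratopathy and synechiae will be compared between treatment groups using chi-square test". In the SAP 11.5 table, the keratopathy and synechiae rows both name the chi-square test in the ITT population. No visit, covariate or baseline term is given.

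The same SAP section compares changes in IOP, OCT and central subfield thickness, BCVA and the VAS symptoms between "groups using ANCOVA, with the baseline level included in the model".

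Protocol 14.4 names a different method for the two binary endpoints: "The presence of keratopathy and synechiae will be compared between treatment groups using logistic regression". It names no baseline covariate for them either.

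On data collection, SAP 5.2 says of the secondary endpoints: "These data were reported at visit 1 (baseline), at visit 2 (after 6 months) and at visit 3 (after 12 months"). Protocol 3.2 gives as an objective "the evaluation of the improvement of side effects due to HLA-B27-associated uveitis such as IOP, cystoid macular edema, keratopathy and synechia", which allows for lesions at entry.

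SAP 13 lists two departures from the protocol. One drops the per-eye relapse analysis. The other reads: "Nonparametric test will be used when the variables are not normally distributed". The change of test for keratopathy and synechiae is neither. SAP 9.2 says that analyses will adjust for site.

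**The concern.** Every patient has had at least one relapse in the year before entry (Protocol 6.2), and Protocol 1.2 lists keratopathy and posterior synechiae among the complications of the disease. Some patients may therefore have a lesion at visit 1. A test of presence at a later visit cannot tell a persisting lesion from a new one, and it sees a resolved lesion only as an absence. Persisting lesions raise the event rate in both arms and shrink the visible difference.

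SAP 11.4.2 also promises to compare the incidence of these complications, but gives neither a method nor a definition of a new case, so that sentence does not fill the gap.

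At stake are the power of two secondary comparisons and their readability if the arms happen to differ at baseline.

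**Working it through.** **The plan's own figures.** The documents give no power, prevalence or incidence for these two endpoints. The only sample-size figure is for relapse count (Protocol 14.7). Normal approximation: n per arm = 2 × (1.96 + 0.84)² × (0.7/0.6)² ≈ 21.4, so 22 per arm or 44. The t-distribution version gives 22.37, so 23 per arm, which reproduces the stated 46. Dropout: 46/0.8 = 57.5, so 58; 60 are recruited. With 20% dropout, 30 × 0.8 = 24 per arm remain.

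**Does the switch from logistic regression cost power?** For 6/30 versus 13/30, Pearson chi-square = 60 × (6×17 − 13×24)² / (30 × 30 × 19 × 41) = 3.774, p = 0.052. The score test of a logistic model with treatment alone is also 3.774. The two methods coincide unless a covariate is added, so any loss comes from omitting baseline.

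**Dilution.** Let b be baseline prevalence, s the proportion of old lesions that persist (equal in both arms), and c the new-lesion rate among patients free at baseline. Then:

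- presence at follow-up = b·s + (1 − b)·c
- difference between arms = (1 − b)(c_placebo − c_active)

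With b = 0.20, s = 0.90 and c = 0.35 versus 0.05, presence is 0.18 + 0.28 = 46% on placebo and 0.18 + 0.04 = 22% on active. Old lesions make up 0.18/0.46 = 39% of placebo events and 0.18/0.22 = 82% of active events. The difference falls from 30 to 24 points.

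**Power.** Simulated at 24 per arm, two-sided 5%, comparing the Pearson chi-square on presence with a Cochran-Mantel-Haenszel test stratified by baseline presence (no continuity correction). The latter stands in for a baseline-adjusted logistic model. All rates are assumptions.

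| New lesions, placebo vs active | Persistence | Baseline prevalence | Expected presence | Unadjusted power | Stratified power |
|---|---|---|---|---|---|
| 35% vs 5% | 90% | 20% | 46% vs 22% | 43% | 62% |
| 35% vs 5% | 90% | 40% | 57% vs 39% | 26% | 40% |
| 35% vs 5% | 90% | 60% | 68% vs 56% | 15% | 22% |
| 20% vs 10% | 90% | 20% | 34% vs 26% | 9% | 12% |
| 20% vs 10% | 90% | 40% | 48% vs 42% | 8% | 9% |
| 20% vs 10% | 50% | 20% | 26% vs 18% | 11% | 11% |
| 35% vs 5% | 30% | 20% | 34% vs 10% | 55% | 55% |
| 35% vs 5% | 30% | 40% | 33% vs 15% | 32% | 31% |

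A second set of assumptions (30 per arm, new lesions 40% vs 10%, prevalence 30%) gives 38% versus 63% if all old lesions persist and 38% versus 46% if 70% persist. With no lesions at baseline the two tests agree (80% each). Stratification helps only when baseline status predicts later status, that is, when s is well above c.

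**Type I error.** With equal new-lesion rates, rejection was 4.5% to 5.6% for both tests across the scenarios run at 23 and 30 per arm.

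**Chance imbalance.** With no treatment effect, 30 per arm, 90% persistence and 20% new lesions in both arms, the arms differ at baseline by 20 points or more in 7% to 16% of trials (prevalence 20% to 50%). Within those trials the unadjusted test is positive about 20% of the time. Over all trials it remains near 5%.

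**The case against.** **The change of method is permitted and costs nothing by itself.** Protocol 14 lets the SAP modify the analysis. A reader might infer that replacing logistic regression with chi-square caused the loss. The documents do not support that: Protocol 14.4 names no baseline term for these endpoints, and without one the two methods give the same score test. This objection stands. What remains of the switch is a documentation gap in SAP 13.

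**Randomisation protects the test.** A reader might infer bias or excess false positives. Overall error is about 5%, so neither follows. The 20% rate applies only to trials already seen to be imbalanced, and those are included in the 5%. It is a problem of interpretation.

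**The large gains need favourable assumptions.** They require a large effect and nearly permanent lesions. Under milder assumptions the gain is 0 to 3 points and both tests have little power. This stands, and it limits any claim about size.

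**Keratopathy is not synechiae.** It is assessed by fluorescein staining (Protocol 5.2), and entry requires at least 8 weeks since the last attack resolved. Nothing in the documents says that staining persists, so the argument is stronger for synechiae. A reader might also infer that presence at month 12 mostly repeats baseline; no figure in the documents shows that for either endpoint.

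**Some affected patients may be excluded.** Exclusion criterion 8 removes patients who cannot be measured accurately, and Protocol 9.2.2 says that extensive posterior synechiae can make flare readings unreliable. That may remove some patients with synechiae, but not old lesions in general.

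**Resolution is part of the objective.** The calculation assumes equal persistence in both arms. If the product also clears old lesions, a presence comparison captures some of that. This is a reason to report resolution separately; it does not justify ignoring baseline.

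**Conclusion.** The point holds as an avoidable loss of precision. The planned comparison discards recorded baseline presence, while the continuous ocular endpoints beside it use theirs. Under the assumptions shown, the gain from using it ranges from nothing to 19 points of power (43% to 62%) at 24 per arm. The documents do not fix where in that range the trial lies, because they give no prevalence, persistence or effect for these lesions. Type I error is not at issue.

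The importance lies between minor and a change that should be made: these are secondary endpoints with no power claim, and the relapse comparison is untouched. The reason to act is that the improvement is free.

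**What to change.** In SAP 11.4.2 and the 11.5 table, replace the chi-square for these two endpoints with logistic regression on presence at month 12, including treatment and baseline presence. Use an exact or Firth version if cells are sparse. Add site, as SAP 9.2 requires, if the data allow. A test stratified by baseline presence is an acceptable simpler choice.

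Report separately, by arm, new lesions among patients free at baseline and resolution among those affected. This also gives the promised incidence comparison a definition. State whether the unit is the eye or the patient.

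Present the baseline term as a new addition, since the protocol does not name one and returning to its wording alone would change nothing. List the change of method in SAP 13.

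The cost is SAP wording, settled before unblinding. Baseline slit-lamp findings are already collected at visit 1.

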6.3 Exclusion Criteria

- 1. Presence of a condition or abnormality that in the opinion of the investigator would compromise the safety of the patient or the quality of the data collected.
- 2. Subjects that have received systemic therapy for uveitis with anti-inflammatory, immunosuppressive or biological drugs in the 30 days before study start.
- 3. Subjects with an anticipated need for systemic anti-inflammatory, immunosuppressive or biological drugs during the 12 months of the study.
- 4. Subjects who received an intravitreal, peribulbar, sub-tenon, periocular injection in the previous 6 months.
- 5. Subjects that are receiving long-term treatment with systemic anti-inflammatory, immunosuppressive or biological drugs for other diseases different from uveitis.
- 6. Women who are taking hormonal contraceptives.
- 7. Subjects that have taken supplements and nutraceuticals in the last 30 days prior to baseline visit. Use of supplements and nutraceuticals will not be admitted during the study.
- 8. Subjects for whom baseline LFM and other ocular evaluations cannot be accurately performed.
- 9. Women who are pregnant or breast-feeding.

The study will be considered completed once the last clinical site will be closed. Participation in this study has no impact on the type of medical care that the patient will receive during the study as well as post-study participation.

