9.2.2 Laser Flare Photometry

Anterior Chamber Flare Assessment and Measurement Kowa LFM 600 and 700

The role of intra-ocular inflammation in driving disruption of blood-aqueous barrier and leading to the spreading of proteins and inflammatory cells into the aqueous humor has been previously established. The Standardization of Uveitis Nomenclature (SUV) system to evaluate and grade this kind of inflammatory leakage (flare) in the anterior chamber (AC) of the eye, ranging from 0 to 4+, is not useful or unreliable to detect and quantify AC

inflammation because the SUV test depends on the subjectivity of the evaluation and on the nonlinear grading of flare at the slit-lamp.

Currently, the only available system to quantitatively and objectively measure (with reproducibility) intra-ocular inflammation is the Kowa Laser Flare Meter (LFM) instrument. Such instrument includes a photomultiplier that amplifies the intensity of the light scattered by small molecules (flare) or larger particles (inflammatory cells) in the aqueous humor. The information is then processed by a computer and the result is expressed in photon counts per millisecond (ph/ms).

LFM instruments quantify back-scattered light both from small molecules and from larger particles such as inflammatory cells. Therefore, LFM measurements may be unreliable in eyes with extensive posterior synechiae or mature cataract due to increased background scattering of light. Seven measurements shall be obtained with LFM. The highest and the lowest LFM values are discarded and the mean and standard deviation of the remaining five LFM readings are automatically calculated. Patients do not experience any pain or discomfort during measurements. Aqueous flare intensity in the range of 2.9–3.9 ph/ms corresponds to healthy individuals between 20 and 40 years of age and they increase slightly with age, reaching 5.0–6.5 ph/ms for patients between 70 and 80 years of age.

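### Synechiae are tested only as present or absent, with no baseline term, so worsening in patients who already have them is missed; the cost depends on how many have them at entry

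*SAP*

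**What the plan says.** SAP 5.2, like Protocol 5.2, defines the synechiae record as "present/absent and if present, involving one or more quadrants; photographs shall be retained to document synechia". SAP 5.2 places these data at Visits 1, 2 and 3.

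The analysis uses less than is recorded. SAP 11.4.2 states: "The presence of keratopathy and synechiae will be compared between treatment groups using chi-square test". The summary table in SAP 11.5 lists "The presence of synechiae (secondary endpoint") with a chi-square test in the ITT population. Neither place gives a baseline term, a visit, or a unit (eye or patient). In the same SAP section, IOP, OCT thickness, BCVA and the VAS symptoms each get an ANCOVA with the baseline level in the model.

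Protocol 14.4 also tests presence only, but by another method: "The presence of keratopathy and synechiae will be compared between treatment groups using logistic regression". It then adds: "The number of quadrants involved by synechiae, when present, will be described". The SAP analysis text does not carry that description over. SAP 13, which lists departures from the protocol analysis, mentions neither the dropped description nor the change of test.

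**The concern.** The objective is improvement in complications of uveitis, and the endpoint is their reduction. For synechiae, the change a product could produce includes stopping an existing adhesion from spreading. Entry requires at least one relapse in the past year, the protocol lists posterior synechiae among the complications of the disease, and synechiae at entry are not a named exclusion. Some patients may therefore start with them. As long as their synechiae do not fully release, they finish as present whether they go from one quadrant to three or stay at one.

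Two faults combine. A comparison of final presence ignores status at entry, so existing synechiae dilute any difference between arms. Reducing quadrants to yes or no also discards progression. Restricting the presence test to patients free of synechiae at baseline repairs the first fault but not the second, because the patients with existing disease are then dropped.

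**Working it through.** **The plan's own figure.** The only sample-size calculation concerns relapse counts: difference 0.6, SD 0.7, 80% power, 5% alpha. The normal formula gives n per arm = 2 × (1.96 + 0.842)² × (0.7/0.6)² = 21.4, so 22. The t-based solution is 22.4, so 23 per arm, or 46 in total, as stated. Dropout: 46/0.8 = 57.5, so 58, and the plan recruits 60. This reproduces but says nothing about synechiae. The documents give no prevalence, incidence, effect or power for them.

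**Assumptions for the illustration (none on synechiae comes from the documents).** 23 per arm; a mean of 2.6 relapses (SD 0.7) in both arms; each relapse adds a quadrant with probability 0.30 on placebo and 0.09 on active (70% less); existing synechiae persist; those affected at entry start with 1 + Binomial(3, 0.25) quadrants; cap of 4.

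**Dilution by hand.** In patients free at entry, final presence is about 1 − 0.7^2.6 = 0.604 on placebo and 1 − 0.91^2.6 = 0.217 on active, a difference of 0.387. If a share π has synechiae at entry, final presence is π + (1 − π)p in each arm, so the difference shrinks to (1 − π) × 0.387: 0.310 at 20% and 0.232 at 40%. The expected difference in new quadrants, 2.6 × (0.30 − 0.09) = 0.55, does not depend on π, apart from the cap.

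Approximate power of the presence test is Φ[(d − 1.96·SE₀)/SE₁], with SE₀ = √(2p̄(1 − p̄)/23) and SE₁ = √((p₀(1 − p₀) + p₁(1 − p₁))/23). At 40%: p₀ = 0.763, p₁ = 0.530, d = 0.232, p̄ = 0.647, SE₀ = 0.141, SE₁ = 0.137. This gives (0.232 − 0.276)/0.137 = −0.32, or 37%.

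**Simulated power under the same assumptions** (repeat runs differ by up to about 5 points):

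| Synechiae at entry | Presence, as planned | Presence, baseline-free patients only | Quadrants, ANCOVA with baseline |
|---|---|---|---|
| 0% | 76% | 76% | 82% |
| 10% | 67% | 72% | 80% |
| 20% | 55% | 66% | 82% |
| 40% | 37% | 53% | 80% |
| 60% | 23% | 40% | 79% |

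**The trial's own effect.** The plan expects 2.0 against 2.6 relapses, which is 0.6/2.6 = 23% fewer. With that as the only effect and the same 0.30 per relapse in both arms, power is about 6 to 13% for either test. At 0.40 per relapse the quadrant analysis reaches only 15 to 17%.

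**Splitting the loss.** A second model (30 per arm, 0.6 new quadrants a year on placebo, rate ratio 0.3, 30% affected at entry) gives:
- final presence: 35%
- final quadrants without baseline: 38%
- new presence in baseline-free patients: 53%
- change in quadrants (Mann-Whitney): 71%
- ANCOVA with baseline: 73%

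Using baseline takes presence from 35% to 53% (18 points). Adding the graded scale takes it from 53% to 73% (20 points). The graded scale without baseline gains almost nothing.

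**The case against.** A reader might infer that most of the power is lost. The documents do not support that as a general statement. It needs a prevalence at entry that they never give and an effect far larger than the planned one. With none at entry the loss is small. In the table, more than half the power goes only at about 40% or above; in the second model, at roughly 20 to 30% or above. This part of the objection stands.

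It also stands that prevalence at entry may be limited. The protocol excludes "Subjects for whom baseline LFM and other ocular evaluations cannot be accurately performed", and its section 9.2.2 warns that "LFM measurements may be unreliable in eyes with extensive posterior synechiae or mature cataract". Extensive cases may be screened out. Limited synechiae, which have room to progress, are not.

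Existing synechiae need not be permanent: the treatment text in Protocol 1.2 says cycloplegics can break them. Presence is then not strictly fixed, but the quadrant analysis stays ahead when release is allowed.

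The recorded scale is uncertain. SAP 5.2 says "present/absent and if present, involving one or more quadrants", which could mean one versus several, and the CRF is not shown. Protocol 14.4 speaks of a number, which points to a count. If the coding is only 0, 1, or 2 and more, ANCOVA still leads the baseline-free presence test: 74% against 68% at 20%, 68% against 53% at 40%.

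Finally, SAP 6.2 says analysis follows the protocol as well as the SAP, and the title of Table 14.2.2.6 is not limited to presence, so the quadrant description could still appear. That would restore a summary, not a comparison of arms.

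**Conclusion.** The concern holds in conditional form. The only planned comparison of synechiae is final presence without baseline, although graded data are recorded, and worsening in patients already affected is not captured. The departure from the protocol's quadrant description is not listed in SAP 13.

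The size is conditional. For a 70% reduction in new quadrants with persistent synechiae, the gain from a baseline-adjusted quadrant analysis is about 6 points with none affected at entry, 27 at 20% and 43 at 40%. For the relapse reduction the trial plans on, neither analysis has useful power. The quadrant scale alone is not the remedy: baseline and grading must be used together.

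Severity is minor to moderate. This is one component of a secondary endpoint with no sample-size basis, but the remedy is cheap.

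**What to change.** Before the blind is broken, amend SAP 11.4.2, SAP 11.5 and Table 14.2.2.6:

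- Compare the number of quadrants with synechiae at Visit 3 between arms, with baseline quadrants as covariate, by ANCOVA or proportional-odds regression. A Wilcoxon test on change in quadrants is an alternative.
- If the CRF codes only one versus several quadrants, use new or worsened synechiae (yes/no), judged from the retained photographs where possible. Judged from full quadrant information, this held about 75% power at every prevalence tried under the 70% scenario.
- State the unit: per eye with allowance for two eyes per patient, or a defined patient-level value. Both eyes are examined, so a 0 to 4 score per patient is not yet defined.
- State the visit, and whether the SAP 5.2 rule that replaces Visit 3 data after a nearby relapse applies to synechiae.
- Include site in the model, as SAP 9.2 requires of the analysis in general; a plain chi-square test does not do this.
- Keep presence/absence as a descriptive summary by visit, restore the protocol's description of quadrants, and list the change in SAP 13.

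The cost is SAP wording and one table. If the CRF holds a quadrant count, no new data are needed; otherwise the photographs may have to be read. The small downside is that a difference in quadrants is harder to state than a percentage with synechiae.
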